3.1.1.2 Stopping criteria for dose escalation during the single dose phase

Escalation to the next dose level will not occur if any of the following criteria are met with the previous dose levels:

- Either an alanine aminotransferase (ALT) / aspartate aminotransferase (AST) level ≥ 3 x upper limit of normal (ULN) at two consecutive time points, or any pattern of liver function test (LFT) abnormalities giving cause for concern, in two or more volunteers on active treatment.

- Evidence of haemolysis as evidenced by the following in two or more volunteers on active treatment.
 - Reticulocyte count of over 5%, and,

At least two of the following:

- A drop in haemoglobin below 10.5 g/dL.
 - Decrease of 25% in haptoglobin. (The value post-dose to be compared with the average of two pre-dose values. The value should also be 15% below the lower limit of normal [LLN]).
 - Increase of 25% in unconjugated bilirubin or lactate dehydrogenase (LDH). (The value post-dose to be compared with the average of two pre-dose values. The value should also be 15% above ULN).
- A platelet count of below $80,000 \times 10^9/L$ confirmed by a repeat test (in the absence of obvious platelet clumping in a peripheral blood film) in two or more volunteers on active treatment.
 - A QTcF >500 ms in two or more volunteers on active substance (QT interval corrected for heart rate by Fridericia method) or a QTcF prolongation >60 ms on average, sustained for more than 30 minutes, ie, present on two contiguous timepoints, in two or more volunteers on active substance based on the results of the continuous readings compared to baseline.
 - Any general safety finding that in the opinion of the Investigator gives cause for concern.
 - Data indicate that at the next proposed dose, the geometric mean plasma C_{max} would be expected to exceed $2.5 \mu M$ or the geometric mean $AUC_{(0-24)}$ would be expected to exceed $18 \mu M.h$. If $AUC_{(0-24)}$ cannot be calculated $AUC_{(0-t)}$ will be used.

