Appendix A Signatures

Appendix B Additional Safety Information

LIST OF SUPPLEMENTS

Supplement N/A

LIST OF ABBREVIATIONS AND DEFINITION OF TERMS

The following abbreviations and special terms are used in this study protocol.

Abbreviation or special term	Explanation
α 1-AT	Alpha 1 – antitrypsin
ACM	Ambulatory cardiac monitoring
A_e	Cumulative amount of unchanged drug excreted into urine
$A_{e,ss}$	A_e at steady state
AE	Adverse event
ALT	Alanine aminotransferase
AMC	7-amino 4-methyl coumarin
AST	Aspartate aminotransferase
ATC	Anatomical therapeutic chemical classification of drug
AUC	Area under the plasma concentration time curve from time zero to infinity
$AUC_{,ss}$	AUC at steady state
$AUC_{(0-t)}$	AUC from time zero to a specified time
$AUC_{(0-t),ss}$	$AUC_{(0-t)}$ at steady state
AZDD	AstraZeneca drug dictionary
BAL	Bronchoalveolar lavage
BMI	Body mass index
C_{12}	Concentration at 12 hours post dose
$C_{12,ss}$	C_{12} at steady state
[REDACTED]	[REDACTED]
CEFTS	Central ECG files transfer and storage; the AstraZeneca central dECG repository
CGG	Clinical genotyping group
CL/F	Apparent plasma clearance following oral drug administration
$CL/F_{,ss}$	CL/F at steady state
CL_R	Renal clearance of drug from plasma
C_{max}	Observed peak or maximum plasma concentration following drug administration
$C_{max,ss}$	C_{max} at steady state

Abbreviation or special term	Explanation
$C_{\min,ss}$	Minimum plasma (trough) drug concentration after repetitive dosing after steady state is achieved, prior to the first dose of the study day
COPD	Chronic obstructive pulmonary disease
CPK	Creatinine phosphokinase
CPMP	Committee for Proprietary Medicinal Products
CPU	Clinical pharmacology unit
CRF	Case report form
CSR	Clinical study report
DMPK	Drug metabolism and pharmacokinetics
DNA	Deoxyribonucleic acid
[REDACTED]	[REDACTED]
dECG	Digital ECG
ECG	Electrocardiogram
Ecode	Enrolment code
EDTA	Ethylenediamine tetra-acetic acid
Ethics Committee	Synonymous to Institutional Review Board and Independent Ethics Committee
EU	European Union
F_e	Fraction of dose excreted unchanged in the urine
$F_{e,ss}$	F_e at steady state
FSH	Follicle stimulating hormone
GCP	Good clinical practice
GGT	Gamma glutamyltransferase
GMP	Good manufacturing practice
HDPE	High-density polyethylene
HELC	Human Exposure Limits Committee
hERG	Human-ether-a-go-go gene
HIV	Human immunodeficiency virus
HR	Heart rate
HRT	Hormone replacement therapy
hsCRP	High sensitivity C-reactive protein

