3. STUDY PLAN AND PROCEDURES

3.1 Overall study design

This Clinical Study Protocol has been subjected to a peer review according to AstraZeneca standard procedures.

This is double blind, randomised, placebo controlled, parallel group, Phase 1 study. Up to four single dose levels, and two multiple dose levels will be studied in two Japanese and two Caucasian cohorts, each comprising of eight healthy volunteers: In each cohort, two single dose levels, and one multiple dose level will be studied, each separated by a washout period (minimum of 7 days), with the intention that parallel cohorts of Japanese and Caucasian healthy volunteers (age and sex matched) are studied concurrently.

Each volunteer will receive two ascending single doses once daily (on Days 1 and 7), followed by multiple doses (twice daily each dose administered 12 hours apart) for 6 days (Days 13-18), and a final single dose on the morning of Day 19 (ie, a total of 15 doses).

Cohorts of Japanese and Caucasian volunteer will receive the same dose of AZD9668, and will be run in parallel as far as is possible.

The intention is that volunteers remain resident in the [REDACTED] from Day -1 until approximately 72 hours after each of the single doses and after the last dose in Visit 4 (ie, from Day -1 to Day 4; Day 6 to Day 10; and Day 12 to Day 22). The volunteers will be allowed home in between the single doses or may stay in the unit at the Investigators discretion. If the dosing schedule is separated further for practical reasons, volunteers will be allowed home, from approximately 72 hours after the last dose in each treatment period. (Note - Further separation of the dosing periods will not affect the 'study day' nomenclature).

Figure 1 shows the study flow chart and Table 1 outlines the assessments at each visit.

Visit 1a (to provide informed consent only) and Visit 1b (enrolment and screening) will take place up to 21 days prior to Visit 2.

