⁷ Telemetry from -1 to 24 hrs post-dose at Visits 2, 3 and 4, and from -1 to 24 hrs post dose on Day 19 (Visit 4).

⁸ Vital signs will be measured at the timepoints shown in Table 2.

⁹ Female volunteers only.

¹⁰ PK sampling times are detailed in Table 3.

¹¹ Urine collections: Pre-dose on Days 1, 7 and 13 and post dose at 0-4, 4-8, 8-12, 12-24, 24-36, 36-48 hrs on Days 1, 7 and 19. On Day 13 at 0-4, 4-8, 8-12 hrs post dose.

¹² Pharmacodynamic (PD) blood sampling times are shown in Table 4.

¹³ Pharmacogenetic (PGx) blood sample to be obtained at any suitable timepoint post dose.

Table 2 ECG and vital signs assessment schedule – Visits 2, 3 and 4

Time (Relative to dosing)
-01:00
00:00
00:30
01:00
01:30
02:00
03:00
04:00
06:00
08:00
12:00
24:00

Paper ECGs, dECGs (if required), and vital signs (ie, sitting blood pressure and pulse) will be performed at the above times at Visits 2 and 3 (single doses) and after the first and last multiple doses (ie on Days 13 and 19 [Visit 4]). Paper ECGs will also be measured at 48 and 72 hours post dose at Visits 2, 3 and 4.

Table 3 Pharmacokinetic sampling schedule

Day	Time (hours - relative to dosing)
1	Pre-dose, 0.25, 0.5, 1, 2, 3, 4, 5, 7, 9, 12, 24, 36, 48, 72 post-dose
7	Pre-dose, 0.25, 0.5, 1, 2, 3, 4, 5, 7, 9, 12, 24, 36, 48, 72 post-dose
13	Pre-dose, 0.25, 0.5, 1, 2, 3, 4, 5, 7, 9, 12 (pre-dose 2), 13, 15 post-dose
14 and 15	Pre-dose (dose 1)
16 and 17	Pre-dose (dose 1), 1 post-dose
18	Pre-dose (dose 1)
19	Pre-dose, 0.25, 0.5, 1, 2, 3, 4, 5, 7, 9, 12, 24, 36, 48, 72 post-dose

Table 4 Pharmacodynamic sampling schedule

Day	Time (hours - relative to dosing)	
	Cohort 1	Cohort 2
1	Pre-dose, 1, 24 post-dose	Pre-dose, 1, 48 post-dose
7	Pre-dose, 1, 48 post-dose	Pre-dose, 1, 48 post-dose
13	Pre-dose (dose 1), 1 post-dose	Pre-dose (dose 1), 1 post-dose

Time (hours - relative to dosing)		
19	Pre-dose, 1, 24 post-dose	Pre-dose, 1, 48 post-dose

Total of 11 blood samples per volunteer in each cohort.

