The proposed single dose levels are 30 mg, 60 mg, 120 mg and 150 mg, although they may change with emerging data from this study. The top dose will be no higher than 150 mg as this is the maximum dose that was administered to healthy volunteers in the AstraZeneca Global SAD/MAD Study and was found to be safe. In addition, modelled PK data from the current study will ensure that the predicted geometric mean C_{max} and $AUC_{(0-24)}$ at the top dose will not exceed 2.5 μM or 18 $\mu\text{M}\cdot\text{h}$, respectively. The multiple doses for both cohorts 1 and 2 will be selected following a safety review meetings using emerging data from the current study and the AstraZeneca Global SAD/MAD Study. The maximum multiple dose will be capped at a total daily dose of 140 mg. In addition, the emerging PK data from the current study will be modelled to ensure that for the highest dose given, the predicted geometric mean exposures (both $AUC_{(0-24),ss}$ and $C_{max,ss}$) will not exceed 2.5 μM or 18 $\mu\text{M}\cdot\text{h}$, respectively.

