3.1.1 Stopping criteria for dose escalation

3.1.1.1 Safety Review Committee

Within each cohort dose escalation will only proceed once dosing has been completed at the previous dose level, however, it is possible that multiple dose (cohort 1) and single dose 1 (cohort 2) may run in parallel. For cohort 1, following completion of the first single dose level, the Investigator will review available safety data (blinded) to confirm that it is safe to proceed with the next single dose level. After the second single dose, a blinded Safety Review Committee (SRC) will meet to review the available safety data from single doses 1 and 2 to determine whether it is safe to proceed with the multiple dose in these individuals and the single dose 1 for cohort 2. The SRC will also review the PK data (up to 24 hours post dose as a minimum) from the single dose 1, and emerging data from the AstraZeneca Global SAD/MAD Study to confirm dose selection. Following the completion of the multiple dose, the SRC will review the available safety data from the multiple dose and the PK data (up to 24 hours post dose as a minimum) from the first two single doses.

For cohort 2 after completion of the first single dose level the SRC will meet to review safety data from the single dose 1 (cohort 2) and the PK data (up to 24 hours post dose) from the single doses in cohort 1 as a minimum. The SRC will then determine whether it is safe to proceed to single dose 2 (cohort 2) and use available PK data, and emerging data from the AstraZeneca Global SAD/MAD Study to confirm the dose. After single dose 2 (cohort 2) a SRC will meet to review the available safety data from single doses 1 and 2 (cohort 2) to determine whether it is safe to proceed to multiple dose (cohort 2) and use the PK data available from single dose 1 (cohort 2) and cohort 1 (both single and multiple doses), and emerging data from the AstraZeneca Global SAD/MAD Study to confirm the dose. The SRC will also meet following the completion of the multiple dose (cohort 2) to review safety data, and PK data if available, for internal information.

Note: All safety and PK data from the current study will be reviewed blinded.

The SRC will be chaired by an AstraZeneca Physician and will comprise the following individuals, as a minimum:

- AstraZeneca study team physician, or nominated deputy.
- AstraZeneca drug safety physician, or nominated deputy.
- AstraZeneca study team pharmacokineticist, or nominated deputy.

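### The single-dose exposure stopping rule substitutes AUC(0-t) for AUC(0-24) against the same 18 µM·h limit with no minimum t, so a volunteer with no usable value at 24 h or later can only be understated

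*Protocol*

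**What the plan says.** The last single-dose criterion in Protocol Section 3.1.1.2 is a forecast. It begins "Data indicate that at the next proposed dose, the geometric mean plasma" and sets limits of 2.5 µM for Cmax and 18 µM·h for AUC(0-24), both as geometric means. If AUC(0-24) "cannot be calculated $AUC_{(0-t)}$ will be used". No separate limit and no minimum t accompany the substitute. The abbreviation list defines AUC(0-t) only as "AUC from time zero to a specified time".

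Table 3 (Section 3.1) gives the sampling times on Days 1 and 7 as "Pre-dose, 0.25, 0.5, 1, 2, 3, 4, 5, 7, 9, 12, 24, 36, 48, 72 post-dose". Volunteers are meant to stay in the unit "until approximately 72 hours after each of the single doses and after the last dose in Visit 4".

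Section 3.1.1.1 says which PK data the Safety Review Committee (SRC) must have. After the second single dose in cohort 1 it needs "PK data (up to 24 hours post dose as a minimum) from the single dose 1". After the first single dose in cohort 2 it needs "PK data (up to 24 hours post dose) from the single doses in cohort 1 as a minimum". For the top dose, Section 3.1 says that "modelled PK data from the current study will ensure that the predicted geometric mean" Cmax and AUC(0-24) stay within the limits.

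**The concern.** The 18 µM·h limit is a safety ceiling; Section 3.2.1 derives it from exposure at the no-effect level in the rat. It applies to exposure over 24 hours. Comparing a shorter area with the same number relaxes the rule, and nothing in the text stops that shorter area being used.

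The direction matters more than the size. Whenever t is under 24 h, the error runs one way, towards allowing the next dose.

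The statistical analysis plan cannot be relied on to settle this. Section 6.4.1 requires it only before database lock, so it need not exist when the escalation decisions are taken. The multiple-dose rule in Section 3.1.1.3 contains no such substitution.

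**Working it through.** The protocol states no figure for this error, so there is none to reproduce.

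**Inputs from the protocol**
- Limit: 18 µM·h on the geometric mean AUC(0-24) (Section 3.1.1.2).
- Sampling: nothing between 12 h and 24 h (Table 3).
- Active volunteers: 6 of 8 in each ethnic cohort (Section 3.4.3). The criteria are judged over all volunteers at a dose level (Section 3.1.1.3), so 6 + 6 = 12.
- LLOQ: 1.00 nM (Section 4.2.1).

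**Assumptions, not in the protocol**
- Half-life of 4, 6, 12 or 18 h, with mono-exponential decline.
- One of the 12 volunteers has a last usable sample at 12 h.
- The fallback is applied volunteer by volunteer.
- The forecast scales observed AUCs in proportion to dose.

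**Step 1: direction.** The area to a time before 24 h cannot exceed the area to 24 h. With no usable value at 24 h or later, t is at most 12 h.

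**Step 2: the volunteer's own ratio.** With k = ln 2 / t½, r = AUC(0-12)/AUC(0-24) = (1 − e^(−12k))/(1 − e^(−24k)).

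**Step 3: the dose-level geometric mean.** One truncated value among 12 multiplies the geometric mean by r^(1/12), so the fall is 1 − r^(1/12).

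**Step 4: at the limit.** If the reported forecast is exactly 18 µM·h, the forecast without truncation is 18 / r^(1/12). Under proportional scaling, this relative error is the same for any dose step.

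| t½ (h) | r | Volunteer's own shortfall | Fall in geometric mean, 1 of 12 | True forecast when 18 is reported (µM·h) |
|---|---|---|---|---|
| 4 | 0.889 | 11% | 0.98% | 18.18 |
| 6 | 0.800 | 20% | 1.84% | 18.34 |
| 12 | 0.667 | 33% | 3.32% | 18.62 |
| 18 | 0.613 | 39% | 3.99% | 18.75 |

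**Step 5: sensitivity**
- First-order absorption (assumed ka 0.5 to 2 per h): A(t) = (1 − e^(−kt))/k − (1 − e^(−ka·t))/ka and r = A(12)/A(24). The fall is 1.1% to 4.8%.
- One ethnic cohort alone, n = 6: 1 − r^(1/6) = 1.9%, 3.7%, 6.5% and 7.8% for the four half-lives.
- A last usable sample before 12 h would make the shortfall larger.

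**Step 6: cases that do no harm**
- 24 h value below the LLOQ: take C24 = 1 nM, so C12 = 2^(12/t½) nM. The area lost is at most (C12 − 1)/k, which is 40.4 nM·h (t½ 4 h) down to 15.3 nM·h (t½ 18 h). That is 0.1% to 0.2% of 18 µM·h.
- t of 36 to 72 h: (1 − e^(−tk))/(1 − e^(−24k)) runs from 1.01 to 1.55, so the substitute overstates and errs on the safe side.
- 24 h value missing with later samples at hand: AUC(0-24) can be interpolated, so the fallback is not needed.

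**The case against.** **Timing.** The PK reviews that Section 3.1.1.1 requires look back at earlier dose levels. When the SRC meets after the second single dose in cohort 1, the 36, 48 and 72 h samples from the first dose have been drawn for days. Harm needs the 24 h value to be unusable and every later sample to be unusable or not yet assayed. This stands, and it makes the case residual. It does not remove the case: the stated minimum is data to 24 h, and a sample that has been drawn may not have been assayed.

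**The 24 h minimum.** It can be read as a practical floor on t. But it describes the data the committee must have, and does not say what to do with a volunteer whose 24 h value is missing. In a review held on 24 h data alone, that value is the only one at or beyond 24 h, so losing it triggers the fallback.

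**Modelling.** Section 3.1 says AUC(0-24) at the top dose is predicted from modelled data. A model could predict it from a profile ending at 12 h, and the effect could then be nil. This stands for the top dose. Still, a provision for an AUC(0-24) that cannot be calculated fits the non-compartmental values of Section 6.1.1.1 better than model output.

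**Per volunteer or per dose level.** The text does not say how the fallback is applied. Per-volunteer use is an assumption of the calculation.

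**Size against noise.** With an assumed between-subject CV of 20% to 40%, the standard error of a 12-volunteer geometric mean is about 6% to 11%. A shift of 1% to 4% would seldom decide anything. The Cmax limit, the 150 mg cap, the Investigator's general-concern criterion and SRC review also remain. All of this is fair and keeps the point minor, although this error always runs the same way.

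**Conclusion.** The point holds in a narrow form. The rule prescribes a substitute for AUC(0-24) against an unchanged limit and sets no minimum t. Where a volunteer has no usable value at 24 h or later at the review, that substitute can only understate exposure. The fall of about 1% to 4% in the dose-level geometric mean depends on the assumed half-lives, truncation at 12 h, exactly one of 12 affected, per-volunteer use, and scaling of observed AUCs.

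A reader might infer three stronger things that the protocol does not support:
- **That 1% to 4% is how often this happens.** No missing-sample rate is given, so no frequency can be derived. That the case is unusual is a judgement from residency to about 72 h and the sampling schedule.
- **That every missing 24 h sample biases the rule.** It does not when later samples are at hand.
- **That the step to 150 mg would pass a true exposure above 18 µM·h.** That step is to rest on modelled AUC(0-24), and the PK required for it comes from the cohort 1 single doses, so scaling up truncated 120 mg values is not the path described.

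This is a minor correction to a safety rule, worth making because the error favours escalation and the remedy costs almost nothing.

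**What to change.** Replace the fallback sentence in Section 3.1.1.2 with:

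> If AUC(0-24) cannot be calculated directly, it will be obtained by interpolation from later samples, or by extrapolation or PK modelling to 24 h; AUC(0-t) will be used unchanged only if t is at least 24 h or the 24 h concentration is below the LLOQ.

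This is one sentence and needs no new samples or data. The cost is slight extra PK work at a review and some uncertainty in the extrapolated slope. A slope fitted to samples up to 12 h may be steeper than the terminal slope, so some understatement can remain. Using the dose group's slope or the PK model limits this.

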3.1.1.3 Stopping criteria for dose escalation during the multiple dose phase

Escalation to the next dose level will not occur if any of the following criteria are met with the previous dose levels:

- Two or more volunteers on active treatment are discontinued because of either an ALT/AST level $\geq 3 \times ULN$ or any pattern of LFT abnormalities giving cause for concern.
- Evidence of haemolysis as evidenced by the following in two or more volunteers on active treatment.
 - Reticulocyte count of over 5%, and,

At least two of the following:

- A drop in haemoglobin below 10.5 g/dL.
 - Decrease of 25% in haptoglobin. (The value post-dose to be compared with the average of two pre-dose values. The value should also be 15% below LLN).
 - Increase of 25% in unconjugated bilirubin or LDH. (The value post-dose to be compared with the average of two pre-dose values. The value should also be 15% above ULN).
- A platelet count of below $80,000 \times 10^9/L$ confirmed by a repeat test (in the absence of obvious platelet clumping in a peripheral blood film) in two or more volunteers on active treatment.
 - A QTcF >500 ms in two or more volunteers on active substance (QT interval corrected for heart rate by Fridericia method) or a QTcF prolongation >60 ms on average, sustained for more than 30 minutes, ie, present on two contiguous timepoints, in two or more volunteers on active substance based on the results of the continuous readings compared to baseline.
 - Any general safety finding that in the opinion of the Investigator gives cause for concern.
 - Data indicate that at the next proposed dose the geometric mean steady state exposure ($C_{\max,ss}$ or $AUC_{(0-24),ss}$) will exceed 18 $\mu M.h$ and 2.5 μM , respectively.

Dosing in an individual volunteer may be discontinued in the multiple dose phase of the study (see Section 3.3.5.1 for criteria).

The stopping criteria refer to all volunteers at a specific dose level. In the event of the need to unblind the data for a given volunteer, or a given cohort, the study design will revert to a single blind study for that volunteer or cohort.

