For cohort 2 after completion of the first single dose level the SRC will meet to review safety data from the single dose 1 (cohort 2) and the PK data (up to 24 hours post dose) from the single doses in cohort 1 as a minimum. The SRC will then determine whether it is safe to proceed to single dose 2 (cohort 2) and use available PK data, and emerging data from the AstraZeneca Global SAD/MAD Study to confirm the dose. After single dose 2 (cohort 2) a SRC will meet to review the available safety data from single doses 1 and 2 (cohort 2) to determine whether it is safe to proceed to multiple dose (cohort 2) and use the PK data available from single dose 1 (cohort 2) and cohort 1 (both single and multiple doses), and emerging data from the AstraZeneca Global SAD/MAD Study to confirm the dose. The SRC will also meet following the completion of the multiple dose (cohort 2) to review safety data, and PK data if available, for internal information.

Note: All safety and PK data from the current study will be reviewed blinded.

Figure 1 Study flow chart

[figure not shown]

Table 1 Study plan

Assessment	Visit 1a	Visit 1b	Visit 2	Visit 3	Visit 4	Visit 5
		Day -21 to -1	Day 1	Day 7	Day 13 to 19	Day 29 (+2 days)
Informed consent / enrolment	X					
Genetic consent	X					
Inclusion/Exclusion criteria		X	X			
Demographics		X				
Medical and surgical history		X				
Concomitant medication		X	X	X	X	X
Physical examination (inc. height and weight)		X	X ^{1,2}			X ²
Alcohol and drugs of abuse screen		X	X	X ³	X ³	X ³
Hepatitis B&C and HIV screen		X				
Safety bloods and urinalysis		X	X ⁴	X ⁴	X ⁴	X
12-Lead ECG (paper)		X	X	X	X ⁵	X
12-Lead ECG (digital)			X ⁶	X ⁶	X ⁶	
Telemetry			X ⁷	X ⁷	X ⁷	
Sitting blood pressure and pulse		X	X ⁸	X ⁸	X ⁸	X
Pregnancy test		X ⁹				
Adverse events		X	X	X	X	X
Randomisation			X			
AZD9668 or placebo administration			X	X	X	
Plasma PK profile			X ¹⁰	X ¹⁰	X ¹⁰	
Full urine collection (PK)			X ¹¹	X ¹¹	X ¹¹	
PD blood sample			X ¹²	X ¹²	X ¹²	
PGx blood sample			X ¹³			

¹ Abbreviated physical examination only.

² Weight only will be measured at this visit.

³ To be performed when volunteer returns to the [REDACTED] between study visits.

⁴ Pre-dose in each dosing period.

⁵ Paper ECGs recorded at the timepoints shown in Table 2, and at 48 and 72 hrs post dose at Visits 2, 3 and 4. If dECGs are to be performed each should be preceded by a paper ECG recording.

⁶ Digital ECGs (if required) will be performed at the times shown in Table 2.

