3.3.5 Discontinuation of subjects from treatment or assessment

3.3.5.1 Criteria for discontinuation

Volunteers may be discontinued from study treatment and assessments at any time. Specific reasons for discontinuing a volunteer from this study are:

- Voluntary discontinuation by the volunteer, who is at any time free to discontinue his/her participation in the study without prejudice to further treatment.
- Safety reasons as judged by the Investigator and/or AstraZeneca.
- Severe non-compliance to protocol as judged by the Investigator and/or AstraZeneca.

- Incorrect enrolment ie, the volunteer does not meet the required inclusion/exclusion criteria for the study.
- Volunteer lost to follow-up.

Dosing will be discontinued in the multiple dosing period (ie, during Visit 4) if the criteria below are met:

- An ALT/AST level ≥ 3 x ULN or any pattern of LFT abnormalities giving cause for concern.
- Evidence of haemolysis as evidenced by the following in two or more volunteers on active treatment.
 - Reticulocyte count of over 5%, and,

At least two of the following:

- A drop in haemoglobin below 10.5 g/dL.
- Decrease of 25% in haptoglobin. (The value post-dose to be compared with the average of two pre-dose values. The value should also be 15% below LLN).
- Increase of 25% in unconjugated bilirubin or LDH. (The value post dose to be compared with the average of two pre dose values. The value should also be 15% above ULN).
- A platelet count of below $80,000 \times 10^9/L$ confirmed by a repeat test (in the absence of obvious platelet clumping in a peripheral blood film) in two or more volunteers on active treatment.
- A QTcF >500 ms in two or more volunteers on active substance (QT interval corrected for heart rate by Fridericia method) or a QTcF prolongation >60 ms on average, sustained for more than 30 minutes, ie, present on two contiguous timepoints, in two or more volunteers on active substance based on the results of the continuous readings compared to baseline.
- Any general safety finding that in the opinion of the Investigator or SRC gives cause for concern.

Specific reasons for discontinuing a volunteer from the genetic research when genetics is a secondary objective of the study are:

- Withdrawal of consent for genetic research. A volunteer may withdraw from this genetic research at any time, independent of any decision concerning participation

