Adverse events and any abnormalities in laboratory tests, vital signs or physical examination of clinical relevance will be followed up until resolution. Volunteers who drop out during the study for reasons other than discontinuation of study drug will be followed up for the planned duration of the study. Abnormalities in laboratory tests and vital signs will be recorded and reported in the laboratory reports and CRFs respectively. Abnormalities in these variables will be identified, analysed and reported in the CSR. Laboratory results that constitute a SAE or lead to discontinuation of the study drug will be recorded and reported as an AE. In addition, any abnormality in laboratory tests, which meet the stopping criteria as described in Section 3.1.1, will be recorded as an AE.

Should an overdose (accidental or deliberate) occur, it must be reported in accordance with the procedures described in Section 8.3, ‘Procedures in case of overdose’, regardless of whether the overdose was associated with any symptom or not. All symptoms associated with the overdose should be reported as AEs.

Should a pregnancy occur, it must be reported in accordance with the procedures described in Section 8.4, ‘Procedures in case of pregnancy’. Pregnancy in itself is not regarded as an AE unless there is a suspicion that an investigational product may have interfered with the effectiveness of a contraceptive medication.

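### The multiple-dose liver stopping rule counts volunteers taken off dosing, not raised ALT/AST, so a rise first found after the Day 19 dose cannot trigger it

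*Protocol*

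**What the plan says.** Protocol Section 3.1.1.3 lists what prevents escalation in the multiple-dose phase. Its liver item is met when "Two or more volunteers on active treatment are discontinued because of either an ALT/AST level" at or above 3×ULN, or because of a liver-test pattern of concern. The verb covers both limbs. The same section says that an individual's dosing may be discontinued and refers to Section 3.3.5.1 for the criteria. That section states: "Dosing will be discontinued in the multiple dosing period (ie, during Visit 4) if the criteria below are met". The first criterion there is a single ALT or AST value at or above 3×ULN.

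The single-dose liver criterion in Section 3.1.1.2 is worded differently. One limb counts ALT/AST at or above 3×ULN when seen twice in a row. The other limb reads: "any pattern of liver function test (LFT) abnormalities giving cause for concern, in two or more volunteers on active treatment". The haemolysis, platelet and QTcF criteria in both phases also count the finding.

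On timing, Section 3.1 ends treatment with "a final single dose on the morning of Day 19 (ie, a total of 15 doses"). Footnote 4 to Table 1 places the safety bloods at Visits 2, 3 and 4 "Pre-dose in each dosing period". The next safety bloods are at Visit 5, Day 29 (+2 days).

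**The concern.** The liver item counts a consequence of the abnormality, stopping the drug, and that consequence is available only while doses remain. After the morning of Day 19 none remain, so a later finding cannot satisfy the item at any size or in any number of volunteers.

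The study has two multiple-dose levels, one per cohort, so this item governs one escalation: from cohort 1's multiple dose to cohort 2's. For haemolysis, platelets and QTcF the protocol gives an automatic stop that does not depend on whether dosing was interrupted. For the liver, that stop is missing exactly when the first scheduled results after multiple dosing arrive. A late rise would have to be caught by the item "Any general safety finding that in the opinion of the Investigator gives cause for concern", by SRC judgement, or by the Principal Investigator's final decision.

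**Working it through.** **1. Does the schedule reproduce the protocol's own count?** Table 1 with footnote 4 gives chemistry at Visit 1b, pre-dose at Visits 2, 3 and 4, and Visit 5: 1 + 1 + 1 + 1 + 1 = 5. Table 6 also gives 5 samples, at 8.5 mL each: 5 × 8.5 = 42.5 mL, as printed. The Table 6 total reproduces too: 49.5 + 260.0 + 10.0 + 42.5 + 8.5 + 15.0 + 8.5 + 65.0 = 459.0 mL. Reading footnote 4 as daily sampling during Visit 4 would need more than the five samples given as the maximum.

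**2. Where do the samples fall relative to multiple dosing?**

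| Sample | Timing | Can it show a multiple-dose effect? | Can it lead to dosing being stopped? |
|---|---|---|---|
| Visit 1b, pre-dose Visits 2 and 3 | before Day 13 | no | not applicable |
| Pre-dose Visit 4 | before the first multiple dose | no | yes, but not for a multiple-dose effect |
| Visit 5 | Day 29 to 31 | yes | no, dosing has ended |

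Scheduled liver results between first and last multiple dose: 0. Scheduled results after the last dose: 1, at 29 − 19 = 10 to 31 − 19 = 12 days. So 0 of 1 scheduled results that could reflect multiple dosing can meet the item by stopping dosing.

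**3. How many volunteers does the rule cover?** Section 3.1.1.3 applies the criteria to all volunteers at a dose level, and Section 3.4.3 allocates 6:2 in each ethnic group. Active volunteers: 6 + 6 = 12.

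**4. What would a finding-based rule do?** The protocol gives no rate of liver rises, so the rates here are assumptions. Let p be the true rate of detected ALT/AST at or above 3×ULN, f the share of rises found before the last dose, and q the rate that counts toward the rule. With independent volunteers,

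P(at least 2 of 12) = 1 − (1 − q)^12 − 12q(1 − q)^11,

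where q = p if the finding is counted and q = p × f under the present wording.

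| Assumed p | Finding counted | Present wording, f = 0.5 | Present wording, f = 0 |
|---|---|---|---|
| 0.05 | 0.118 | 0.035 | 0 |
| 0.10 | 0.341 | 0.118 | 0 |
| 0.20 | 0.725 | 0.341 | 0 |
| 0.30 | 0.915 | 0.557 | 0 |

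The scheduled samples alone give f = 0. A value above 0 needs unscheduled bloods during dosing.

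**5. Does the SRC timetable close the gap?** Under Section 3.1.1.1 the SRC reviews the safety data available after cohort 1's multiple dose, with no requirement to wait for Visit 5. For the meeting that clears cohort 2's multiple dose, the section names safety data from cohort 2's single doses but only PK data from cohort 1.

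**The case against.** **Discontinuation could mean leaving the study.** Section 3.3.5.1 allows discontinuation from treatment and assessments at any time, so a volunteer might be discontinued after Day 19. Section 4.7.1.2 says "Adverse events and any abnormalities in laboratory tests, vital signs or physical examination of clinical relevance will be followed up until resolution", but that does not exclude this reading, because Section 3.3.5.2 provides for follow-up of adverse events in volunteers who have discontinued. This point is fair as far as it goes. It does not rescue the rule: Section 3.1.1.3 ties discontinuation in this phase to dosing, and at Visit 5 no scheduled assessment remains to be discontinued.

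**Discretion is a real backstop.** The Investigator-opinion item is itself a listed bar to escalation, the SRC includes a drug safety physician, and the Principal Investigator settles disagreements in the volunteers' interest. Half of the liver item is already a matter of judgement. All this stands, and nothing in the protocol suggests that two clear rises would be ignored. But the protocol sets objective limits so that escalation does not rest on opinion alone, and the 3×ULN limb is such a limit.

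**The larger gap is the sampling.** Haemolysis and platelets rely on the same bloods and also have no scheduled result during multiple dosing; their advantage is one draw at Visit 5. Rewording will not reveal a rise that resolves before Day 29. Both points are correct. They argue for adding samples as well, not for keeping a rule that ignores the one result the schedule does provide.

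**The rule is strict during dosing.** One value at the limit stops a volunteer's dosing, against two consecutive time points in the single-dose phase. That is right, and it confines the gap to rises found after the last dose.

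**Conclusion.** The concern holds and should be fixed. As worded, the multiple-dose liver criterion cannot be met by a rise first found after the Day 19 dose. On the protocol's schedule the only liver result that could reflect multiple dosing comes 10 to 12 days after that dose, so the criterion has no scheduled result on which it can act. The gap affects one escalation decision and up to 12 active volunteers at the dose level. It is limited to late findings, and discretionary review remains.

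This rests on reading discontinuation as stopping dosing, which Sections 3.1.1.3 and 3.3.5.1 support, and on there being no unscheduled chemistry during Days 13 to 19. The trigger probabilities are illustrations under assumed rates; the conclusion does not depend on them.

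**What to change.** Reword the liver item in Section 3.1.1.3 so that escalation is barred if two or more active volunteers have ALT or AST at or above 3×ULN, or a liver-test pattern judged worrying, at any time from the first multiple dose through follow-up, whether or not dosing was stopped. Add a sentence to Section 3.1.1.1 requiring the SRC to apply this to cohort 1's liver results from after the last dose before cohort 2 starts its multiple dose. The single-value threshold is unchanged.

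The text cost is one item and one sentence. The time cost depends on overlap. Section 3.1.1.1 says "it is possible that multiple dose (cohort 1) and single dose 1 (cohort 2) may run in parallel". If cohort 2's Day 1 falls on cohort 1's Day 13 to 19, cohort 2's Day 13 falls 12 days later, on cohort 1's Day 13 + 12 = 25 to 19 + 12 = 31. Waiting for the Visit 5 draw on Day 29 to 31 then costs at most 31 − 25 = 6 days and at least 0, plus laboratory turnaround. Section 3.1 also states a minimum 7-day washout, longer than the Day 1, 7 and 13 spacing; wider spacing would shorten the wait.

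A liver sample during multiple dosing and another before discharge on Day 22, while volunteers are resident, would be a further gain. At 8.5 mL each these would need adding to Table 6. The rewording is sound without them.
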